8.6 Efficacy analyses

This section addresses the analyses to be conducted on the primary, secondary and exploratory efficacy variables.

The FAS will be the primary population for all efficacy related endpoints and the primary objective. Sensitivity analyses on all subjects who received at least one dose of AFM13 and had at least one post-baseline efficacy assessment and on PP set will be conducted to support the results of the primary analysis, when deemed necessary (ie, if the number of subjects in these populations is different compared to the FAS).

Each efficacy endpoint will be derived separately for IRC and Investigator. Consequently, endpoints using IRC assessments, will be derived using only responses provided by IRC regardless of Investigator responses. Similarly, endpoints using Investigator assessments will be derived using only responses provided by Investigator regardless of IRC responses.

8.6.1 Analysis methods

8.6.1.1 Multiplicity

Not applicable.

8.6.1.2 Treatment by center interaction analysis (multi-center study)

Not applicable.

8.6.1.3 Overall response date of assessment

If the date of assessment of overall response is not recorded/collected in the CRF then this will be assigned to the maximum of all assessments dates which belongs to the disease assessment visit.

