8.6.2 Analysis of efficacy endpoints

The primary endpoint is based on the IRC PET-CT-based metabolic responses. Secondary endpoints are based

Final Analysis Statistical Analysis Plan (SAP)

on IRC CT based radiologic responses and on Investigator (CT or FDG-PET (=PET-CT)) responses.

Overall response

Within each visit an overall response will be determined by the IRC and Investigator on CT-based radiographic responses and FDG-PET (=PET-CT) based metabolic responses separately utilizing the modified Lugano Classification revised staging system for malignant lymphoma (Cheson 2014) for Cohorts A and B (PTCL) and the Olsen Criteria (Olsen 2011) for Cohort C (TMF).

Subjects who cannot be evaluated for response will be categorized as not evaluable (NE).

Best overall response (BOR)

The best overall response is the best response recorded from the start of the treatment until disease progression/recurrence or death. All disease responses obtained after progressive disease, start of new anti-cancer therapy or a transplant are excluded from the best overall response. Best is defined as the first response when all a subject's response assessments are sorted by complete response/complete radiologic response/complete metabolic response (CR), partial response/partial remission/partial metabolic response (PR), stable disease/no metabolic response (SD), pseudoprogression, progressive disease/progressive metabolic disease (PD), not evaluable (NE).

The subject's best response assignment will depend on the achievement of the measurement criteria (confirmation is not required). BOR will be summarized using a frequency table by cohort. For Cohorts A and B, BOR is derived for radiographic (using only CT-based responses) and metabolic responses (using only FDG-PET (=PET-CT) based responses) separately.

Overall response rate (ORR)

ORR is calculated as the proportion of subjects with a CR or PR. Subjects without at least one post-baseline response assessment will be treated as non-responders.

ORR and Pearson-Clopper 95% confidence interval (CI) will be displayed separately for CT-based response and FDG-PET (=PET-CT) based response. CR and PR rates and their Pearson-Clopper 95% CI will be also displayed separately.

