As the study design is based on a Simon's two stage design (See Section 5), an exact binomial test will be performed to analysed the ORR of the Cohorts A and C at the final analysis only. The one-sided p-value will be displayed. The tested hypotheses are as follows for each cohort:

Cohort A: $H_0: p \leq 0.25$

$H_1: p > 0.25$

Cohort C: $H_0: p \leq 0.05$

$H_1: p > 0.05$

For all response assessments, swimmer plots will be presented. All response assessments will be also listed.

The above analyses (overall response, BOR and ORR) will be performed for each cohort and for:

Response evaluator	Population of analysis	Analysis order
IRC	FAS	Primary analysis
IRC	FAS with at least one post-baseline efficacy assessment	Sensitivity analysis, if deemed necessary (based on the number of subjects included in that population after the Classification Meeting)
IRC	COVID analysis set	Sensitivity analysis, if deemed necessary (based on the number of subjects included in that population after the Classification Meeting)
IRC	PP set	Sensitivity analysis, if deemed necessary (based on the number of subjects included in that population after the Classification Meeting)
Investigator	FAS	Secondary analysis
██████████	████████████████████	██ ██ ██

These analyses will be also repeated for the subgroups defined in Section 8.8.5 for the FAS.

Duration of response (DOR)

The DOR is defined as time from first assessment of PR or CR to the first assessment of progressive disease or death due to any cause separately for IRC and Investigator using respectively only IRC or Investigator assessments. DOR will be censored for IRC assessments using Table 1 and Investigator assessments using Table 3 when analyses are performed on FAS or PP set. The Table 2 and Table 4 will be used when the analyses are performed on the COVID analysis set:

Final Analysis Statistical Analysis Plan (SAP)

Table 1: Independent Review Committee Assessments (IRC) Censoring Rules

Event	Event or censored date	Event or censored
Progression (as determined by IRC)	Date of progression (as determined by IRC)	Event
Death due to any cause	Date of death	Event
PD (as determined by IRC) or death after 1 missed assessment (ie, ≥ 59 days between 2 assessments until Cycle 4 and ≥ 87 days from Cycle 5)	Date of PD (as determined by IRC) or death	Event

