PD (as determined by IRC) or death after 2 or more missed assessments (ie, ≥ 118 days between 2 assessments until Cycle 4 and ≥ 174 days from Cycle 5)	Date of last disease assessment before missed assessments	Censored
No baseline tumour assessment	Date of first study drug	Censored
No post-baseline response assessment	Date of first study drug	Censored
Start of new anti-cancer therapy before progression (as determined by IRC) or death	Date of last disease assessment prior to new anti-cancer therapy *	Censored
Transplant before progression (progression as determined by IRC) or death or start of new anti-cancer therapy	Date of last disease assessment prior to date of transplant	Censored
No progression determined by IRC or death	Date of last disease assessment	Censored

Note: Only disease assessments provided to IRC are included in the analysis.

* The new anti-cancer therapy information is only collected on the “Survival follow-up” page but no date is collected. Consequently, it is assumed that the new therapy starts between the follow-up where the question “Did the patient start any new anti-cancer therapies?” is “Yes” and the previous follow-up. The subject will be censored at the last disease assessment prior or on this previous visit.

Final Analysis Statistical Analysis Plan (SAP)

[REDACTED]	[REDACTED]	[REDACTED]
[REDACTED]	[REDACTED]	[REDACTED]
[REDACTED]	[REDACTED]	[REDACTED]
[REDACTED]	[REDACTED]	[REDACTED]
[REDACTED]	[REDACTED]	[REDACTED]
[REDACTED]	[REDACTED]	[REDACTED]
[REDACTED]	[REDACTED]	[REDACTED]
[REDACTED]	[REDACTED]	[REDACTED]
[REDACTED]	[REDACTED]	[REDACTED]
[REDACTED]	[REDACTED]	[REDACTED]
[REDACTED]	[REDACTED]	[REDACTED]
[REDACTED]	[REDACTED]	[REDACTED]
[REDACTED]	[REDACTED]	[REDACTED]
[REDACTED]	[REDACTED]	[REDACTED]
[REDACTED]	[REDACTED]	[REDACTED]
[REDACTED]	[REDACTED]	[REDACTED]
[REDACTED]	[REDACTED]	[REDACTED]
[REDACTED]	[REDACTED]	[REDACTED]

Final Analysis Statistical Analysis Plan (SAP)

* The new anti-cancer therapy information is only collected on the “Survival follow-up” page but no date is collected. Consequently, it is assumed that the new therapy starts between the follow-up where the question “Did the patient start any new anti-cancer therapies?” is “Yes” and the previous follow-up. The subject will be censored at the last disease assessment prior or on this previous visit.

Table 3: Investigator Assessments Censoring Rules

Event	Event or censored date	Event or censored

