11 APPENDIX A

For each disease assessment visit, the visit name will be derived as follows:

Step 1: Determine the minimum and maximum dates per visit as follows:

For Lugano (within the same disease assessment visit):

DateINF = MIN (

TU.TUDTC (Imaging (modified Lugano)),
TR.TRDTC (Imaging (modified Lugano)),
TU.TUDTC (New Lesions (modified Lugano)),
TR.TRDTC (New Lesions (modified Lugano)),
TU.TUDTC (Tissue Sites Involved),
TR.TRDTC (Tissue Sites Involved),
TU.TUDTC (FDG-PET),
TR.TRDTC (FDG-PET),
PR.PRDTC (FDG-PET))

DateSUP = MAX (

TU.TUDTC (Imaging (modified Lugano)),
TR.TRDTC (Imaging (modified Lugano)),
TU.TUDTC (New Lesions (modified Lugano)),
TR.TRDTC (New Lesions (modified Lugano)),
TU.TUDTC (Tissue Sites Involved),
TR.TRDTC (Tissue Sites Involved),
TU.TUDTC (FDG-PET),
TR.TRDTC (FDG-PET),
PR.PRDTC (FDG-PET))

Final Analysis Statistical Analysis Plan (SAP)

For Olsen (within the same disease assessment visit):

DateINF = MIN (
TU.TUDTC [Imaging (Olsen)],
TR.TRDTC [Imaging (Olsen)],
TU.TUDTC (New Lesions (Olsen)),
TR.TRDTC (New Lesions (Olsen)),
FA.FADTC (TNMB Staging),
QS.QSDTC (mSWAT),
QS.QSDTC (CAILS),
LB.LBDTC (Flow cytometry for Olsen criteria),
PR.PRSTDTC (Lesion Photography),
PR.PRSTDTC (Biospy (Olsen criteria)),
MI.MIDTC (Biospy (Olsen criteria))

DateSUP = MAX (
TU.TUDTC [Imaging (Olsen)],
TR.TRDTC [Imaging (Olsen)],
TU.TUDTC (New Lesions (Olsen)),
TR.TRDTC (New Lesions (Olsen)),
FA.FADTC (TNMB Staging),
QS.QSDTC (mSWAT),
QS.QSDTC (CAILS),
LB.LBDTC (Flow cytometry for Olsen criteria),
PR.PRSTDTC (Lesion Photography),
PR.PRSTDTC (Biospy (Olsen criteria)),
MI.MIDTC (Biospy (Olsen criteria))

Final Analysis Statistical Analysis Plan (SAP)

Step 2: Assign the visit name as follows:

If $(SV.SVSTDTC - 7 \leq DateINF \leq SV.SVSTDTC + 7)$

or $(SV.SVSTDTC - 7 \leq DateSUP \leq SV.SVSTDTC + 7)$

or $(DateINF < SV.SVSTDTC - 7 \text{ AND } DateSUP > SV.SVSTDTC + 7)$ then AVISIT = SV.VISIT;

Else AVISIT = "Unscheduled".

Notes:

- Visits planned per protocol to have disease assessments are considered from SV.
- If at least one assessment of the disease assessment visit is within the time-window then all the assessments are assigned to the visit.

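### A missing overall-response date is set to the latest date of the visit for progression as well as for response, so an imputed PD is dated at its last component rather than at first evidence

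*SAP*

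**What the plan says.** SAP 8.6.1.3 applies "If the date of assessment of overall response is not recorded/collected in the CRF". The date is then "assigned to the maximum of all assessments dates which belongs to the disease assessment visit". The section gives this one rule and does not divide it by type of response.

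PD is one of the response categories. The ranking used for best overall response in SAP 8.6.2 ends with "progressive disease/progressive metabolic disease (PD), not evaluable (NE"), and the same section states: "Within each visit an overall response will be determined by the IRC and Investigator".

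DOR is defined in SAP 8.6.2 as "time from first assessment of PR or CR to the first assessment of progressive disease or death due to any cause". Table 1 (IRC) dates the event at "Date of progression (as determined by IRC"), and Table 3 does the same for the Investigator. Neither table says which component date counts as the date of progression. The two tables rest on different data. Table 1 carries the remark "Note: Only disease assessments provided to IRC are included in the analysis", while Table 3 uses assessments recorded in the CRF.

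Appendix A lists the dates that make up a disease assessment visit. For Lugano these are imaging, new lesions, tissue sites and FDG-PET. For Olsen they are imaging, new lesions, TNMB staging, mSWAT, CAILS, flow cytometry, photography and biopsy. It attaches the group to a scheduled visit with a window of 7 days either side, and adds: "If at least one assessment of the disease assessment visit is within the time-window then all the assessments are assigned to the visit".

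**The concern.** For CR or PR the latest date is the cautious choice, because it starts the DOR clock only when all components are in. For PD the same choice works the other way. DOR ends at the first assessment of progression, and if one component shows progression before the others are done, the latest date puts the end of response after its first evidence. A skin score showing progression, followed some days later by a scan or biopsy in the same visit, would be dated by the scan or biopsy.

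What is at stake is the dating of DOR, a secondary endpoint that supports the response rate in a single-arm trial. There is no control arm in which the same dating rule would act equally. Cohort C has the most kinds of component, so its dates have the most opportunity to differ. Primary ORR, deaths and dates that were recorded are not directly affected.

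**Working it through.** The plan states no expected DOR, missing-date rate or component spread, so there is no figure to reproduce. The direction follows from date algebra, and the size can only be illustrated.

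**Notation.** For the first response visit, let R0 and R1 be the earliest and latest component dates, with spread sR = R1 − R0. For the PD visit, let P0 and P1 be the earliest and latest dates, with spread sP = P1 − P0. Let Pe be the date of the earliest component showing progression, so P0 ≤ Pe ≤ P1.

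**DOR under SAP 8.6.1.3 with both dates imputed:** P1 − R1.

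**Comparison 1: response at latest date, PD at earliest evidence.** The difference is (P1 − R1) − (Pe − R1) = P1 − Pe. This lies between 0 and sP and is never negative. It equals sP when the first component of the visit is the one showing progression.

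**Comparison 2: earliest date of the visit for both events.** The difference is (P1 − R1) − (P0 − R0) = sP − sR.

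| sR (days) | sP (days) | SAP rule minus earliest for both | SAP rule minus response latest, PD earliest |
|---|---|---|---|
| 0 | 7 | +7 | +7 |
| 0 | 14 | +14 | +14 |
| 14 | 14 | 0 | +14 |
| 14 | 0 | −14 | 0 |

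The last column takes Pe = P0. If only the PD date is missing, the change from earliest dating is +sP. If only the response date is missing, it is −sR. In a simulation of 400,000 pairs with both dates missing and sR and sP independent and uniform on 0 to S, the mean of sP − sR was 0.00 days for S = 7 and −0.01 days for S = 14. DOR was longer in about half of the pairs.

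**Illustrative size for comparison 1.** Assume sP is uniform on 0 to S, Pe = P0, and a fraction f of PD dates is missing. The mean shift over all PD events is f × S/2.

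| f | S = 7 | S = 14 |
|---|---|---|
| 10% | 0.35 days | 0.7 days |
| 25% | 0.88 days | 1.75 days |
| 50% | 1.75 days | 3.5 days |
| 100% | 3.5 days | 7.0 days |

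Both S and f are assumptions. Taking Pe = P0 gives the largest shift for a given spread.

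**Does Appendix A cap the spread?** No. It takes the earliest and latest dates of components that already belong to one disease assessment visit, and uses the window only to give that visit its name. It also provides for a group that starts more than 7 days before the scheduled visit and ends more than 7 days after it. The 14-day width is therefore neither a limit on sP nor an estimate of it.

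**The case against.** The strongest points on the other side are these.

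- **The rule delays the start of DOR as well.** This stands. A reader might infer that every affected subject's DOR is lengthened. The documents do not support that: relative to earliest dating of both events the net effect is sP − sR, which can be negative, and if only the response date is missing DOR can only shorten. The lengthening is general only relative to dating response late and PD at first evidence.
- **The rule may not reach the IRC-based endpoint.** Its trigger is a date absent from the CRF, whereas IRC-based DOR uses IRC assessments only and the IRC's own progression date. This stands as an open question. Investigator-assessed DOR is the clear target.
- **Another section may deal with it.** The SAP contents list 7.1 on derived variables and 7.2.2 on missing or incomplete dates, and the body of section 7 is not visible in the public copy. A separate rule for PD there cannot be excluded.
- **Overall response is a composite determined per visit, so dating it when the visit is complete is coherent.** This is a fair convention, and the visible text does not say that PD is established at its first component. But DOR ends at the first assessment of progression, which fits earliest evidence better than the last component. The objection also warns against defaulting to the earliest date of the visit, which could put PD before any component showed it.
- **The effect is small.** Disease assessments are 8 and then 12 weeks apart (56 and 84 days), which already makes progression dates coarse, and DOR is summarised by Kaplan-Meier estimates without a test. This stands and limits the weight of the point.

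**Conclusion.** The point holds in a limited form. As visible, SAP 8.6.1.3 has no separate provision for PD, so an imputed PD takes the last component date. DOR is then longer, by up to the date spread within the PD visit, than with response at the latest date and PD at earliest evidence. If the response date is imputed as well, the net effect relative to earliest dating of both may be positive, zero or negative.

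No size can be taken from the documents. Under the assumed uniform 0 to 14 day spread with 10% to 50% of PD dates missing, the mean shift is about 0.7 to 3.5 days over PD events. It would be close to nil if few dates are missing.

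A reader might treat 14 days as the maximum and set it against the 3-month median PFS in protocol 1.2.1. Neither step is supported. The window does not bound the spread, and the 3 months is PFS in PTCL, quoted as a low-end estimate, not DOR in responders or in TMF. No percentage of DOR should be quoted.

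A later PD date could also carry a gap past the 118-day or 174-day limits in Tables 1 and 3 and turn an event into a censored time; this was not quantified. This is a minor point, worth settling before database lock.

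**What to change.** Amend SAP 8.6.1.3 so that, when the overall-response date is missing:

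- CR, PR and SD take the latest component date of the visit, as now.
- PD takes the earliest date of a component showing progression. Only if that component cannot be identified does PD take the earliest date of the visit, with a note that this is conservative for DOR.
- The text says whether the rule applies to IRC data or only to Investigator assessments from the CRF, and is aligned with section 7.2.2.

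The cost is a sentence or two and minor programming, since Appendix A already derives the earliest and latest dates of each visit; the date of the component showing progression would have to be added. The downside is that DOR may be a few days shorter in affected subjects.

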8.6.1.4 Derivation of post-baseline disease assessments visits

In the CRF, the post-baseline disease assessments are not linked to study visits. Consequently, this will be performed by programming as per APPENDIX A.

8.6.2 Analysis of efficacy endpoints

The primary endpoint is based on the IRC PET-CT-based metabolic responses. Secondary endpoints are based

Final Analysis Statistical Analysis Plan (SAP)

on IRC CT based radiologic responses and on Investigator (CT or FDG-PET (=PET-CT)) responses.

Overall response

Within each visit an overall response will be determined by the IRC and Investigator on CT-based radiographic responses and FDG-PET (=PET-CT) based metabolic responses separately utilizing the modified Lugano Classification revised staging system for malignant lymphoma (Cheson 2014) for Cohorts A and B (PTCL) and the Olsen Criteria (Olsen 2011) for Cohort C (TMF).

Subjects who cannot be evaluated for response will be categorized as not evaluable (NE).

Best overall response (BOR)

The best overall response is the best response recorded from the start of the treatment until disease progression/recurrence or death. All disease responses obtained after progressive disease, start of new anti-cancer therapy or a transplant are excluded from the best overall response. Best is defined as the first response when all a subject's response assessments are sorted by complete response/complete radiologic response/complete metabolic response (CR), partial response/partial remission/partial metabolic response (PR), stable disease/no metabolic response (SD), pseudoprogression, progressive disease/progressive metabolic disease (PD), not evaluable (NE).

The subject's best response assignment will depend on the achievement of the measurement criteria (confirmation is not required). BOR will be summarized using a frequency table by cohort. For Cohorts A and B, BOR is derived for radiographic (using only CT-based responses) and metabolic responses (using only FDG-PET (=PET-CT) based responses) separately.

Overall response rate (ORR)

ORR is calculated as the proportion of subjects with a CR or PR. Subjects without at least one post-baseline response assessment will be treated as non-responders.

ORR and Pearson-Clopper 95% confidence interval (CI) will be displayed separately for CT-based response and FDG-PET (=PET-CT) based response. CR and PR rates and their Pearson-Clopper 95% CI will be also displayed separately.

As the study design is based on a Simon's two stage design (See Section 5), an exact binomial test will be performed to analysed the ORR of the Cohorts A and C at the final analysis only. The one-sided p-value will be displayed. The tested hypotheses are as follows for each cohort:

Cohort A: $H_0: p \leq 0.25$

$H_1: p > 0.25$

Cohort C: $H_0: p \leq 0.05$

$H_1: p > 0.05$

For all response assessments, swimmer plots will be presented. All response assessments will be also listed.

The above analyses (overall response, BOR and ORR) will be performed for each cohort and for:

Response evaluator	Population of analysis	Analysis order
IRC	FAS	Primary analysis
IRC	FAS with at least one post-baseline efficacy assessment	Sensitivity analysis, if deemed necessary (based on the number of subjects included in that population after the Classification Meeting)
IRC	COVID analysis set	Sensitivity analysis, if deemed necessary (based on the number of subjects included in that population after the Classification Meeting)
IRC	PP set	Sensitivity analysis, if deemed necessary (based on the number of subjects included in that population after the Classification Meeting)
Investigator	FAS	Secondary analysis
██████████	████████████████████	██ ██ ██

These analyses will be also repeated for the subgroups defined in Section 8.8.5 for the FAS.

Duration of response (DOR)

The DOR is defined as time from first assessment of PR or CR to the first assessment of progressive disease or death due to any cause separately for IRC and Investigator using respectively only IRC or Investigator assessments. DOR will be censored for IRC assessments using Table 1 and Investigator assessments using Table 3 when analyses are performed on FAS or PP set. The Table 2 and Table 4 will be used when the analyses are performed on the COVID analysis set:

Final Analysis Statistical Analysis Plan (SAP)

Table 1: Independent Review Committee Assessments (IRC) Censoring Rules

Event	Event or censored date	Event or censored
Progression (as determined by IRC)	Date of progression (as determined by IRC)	Event
Death due to any cause	Date of death	Event
PD (as determined by IRC) or death after 1 missed assessment (ie, ≥ 59 days between 2 assessments until Cycle 4 and ≥ 87 days from Cycle 5)	Date of PD (as determined by IRC) or death	Event
PD (as determined by IRC) or death after 2 or more missed assessments (ie, ≥ 118 days between 2 assessments until Cycle 4 and ≥ 174 days from Cycle 5)	Date of last disease assessment before missed assessments	Censored
No baseline tumour assessment	Date of first study drug	Censored
No post-baseline response assessment	Date of first study drug	Censored
Start of new anti-cancer therapy before progression (as determined by IRC) or death	Date of last disease assessment prior to new anti-cancer therapy *	Censored
Transplant before progression (progression as determined by IRC) or death or start of new anti-cancer therapy	Date of last disease assessment prior to date of transplant	Censored
No progression determined by IRC or death	Date of last disease assessment	Censored

Note: Only disease assessments provided to IRC are included in the analysis.

* The new anti-cancer therapy information is only collected on the “Survival follow-up” page but no date is collected. Consequently, it is assumed that the new therapy starts between the follow-up where the question “Did the patient start any new anti-cancer therapies?” is “Yes” and the previous follow-up. The subject will be censored at the last disease assessment prior or on this previous visit.

Final Analysis Statistical Analysis Plan (SAP)

[REDACTED]	[REDACTED]	[REDACTED]
[REDACTED]	[REDACTED]	[REDACTED]
[REDACTED]	[REDACTED]	[REDACTED]
[REDACTED]	[REDACTED]	[REDACTED]
[REDACTED]	[REDACTED]	[REDACTED]
[REDACTED]	[REDACTED]	[REDACTED]
[REDACTED]	[REDACTED]	[REDACTED]
[REDACTED]	[REDACTED]	[REDACTED]
[REDACTED]	[REDACTED]	[REDACTED]
[REDACTED]	[REDACTED]	[REDACTED]
[REDACTED]	[REDACTED]	[REDACTED]
[REDACTED]	[REDACTED]	[REDACTED]
[REDACTED]	[REDACTED]	[REDACTED]
[REDACTED]	[REDACTED]	[REDACTED]
[REDACTED]	[REDACTED]	[REDACTED]
[REDACTED]	[REDACTED]	[REDACTED]
[REDACTED]	[REDACTED]	[REDACTED]
[REDACTED]	[REDACTED]	[REDACTED]

Final Analysis Statistical Analysis Plan (SAP)

* The new anti-cancer therapy information is only collected on the “Survival follow-up” page but no date is collected. Consequently, it is assumed that the new therapy starts between the follow-up where the question “Did the patient start any new anti-cancer therapies?” is “Yes” and the previous follow-up. The subject will be censored at the last disease assessment prior or on this previous visit.

Table 3: Investigator Assessments Censoring Rules

Event	Event or censored date	Event or censored
Progression (as determined by Investigator)	Date of progression (as determined by Investigator)	Event
Death due to any cause	Date of death	Event
PD (as determined by Investigator) or death after 1 missed assessment (ie, \geq 59 days between 2 assessments until Cycle 4, \geq 87 days from Cycle 5 and \geq 122 days from Survival Follow-up)	Date of PD (as determined by Investigator) or death	Event
PD (as determined by Investigator) or death after 2 or more missed assessments (ie, \geq 118 days between 2 assessments until Cycle 4, \geq 174 days from Cycle 5 and \geq 244 days from Survival Follow-up)	Date of last disease assessment or date of last survival contact (for Survival Follow-up) before missed assessments	Censored
No baseline tumour assessment	Date of first study drug	Censored
No post-baseline response assessment	Date of first study drug	Censored
Start of new anti-cancer therapy before progression (as determined by Investigator) or death	Date of last disease assessment or date of last survival contact (for Survival Follow-up) prior to new anti-cancer therapy *	Censored

Final Analysis Statistical Analysis Plan (SAP)

Event	Event or censored date	Event or censored
Transplant before progression (progression as determined by Investigator) or death or start of new anti-cancer therapy	Date of last disease assessment or date of last survival contact (for Survival Follow-up) prior to date of transplant	Censored
No progression determined by Investigator or death	Date of last disease assessment or date of last survival contact (for Survival Follow-up)	Censored

Note: Only disease assessments recorded in the CRF are included in the analysis.

* The new anti-cancer therapy information is only collected on the “Survival follow-up” page but no date is collected. Consequently, it is assumed that the new therapy starts between the follow-up where the question “Did the patient start any new anti-cancer therapies?” is “Yes” and the previous follow-up. The subject will be censored at the last disease assessment prior or on this previous visit.

Final Analysis Statistical Analysis Plan (SAP)

[REDACTED]

[REDACTED]	[REDACTED]	[REDACTED]
[REDACTED]	[REDACTED]	[REDACTED]
[REDACTED]	[REDACTED]	[REDACTED]
[REDACTED]	[REDACTED]	[REDACTED]
[REDACTED]	[REDACTED]	[REDACTED]
[REDACTED]	[REDACTED]	[REDACTED]
[REDACTED]	[REDACTED]	[REDACTED]
[REDACTED]	[REDACTED]	[REDACTED]
[REDACTED]	[REDACTED]	[REDACTED]
[REDACTED]	[REDACTED]	[REDACTED]

Final Analysis Statistical Analysis Plan (SAP)

[REDACTED]	[REDACTED]	[REDACTED]
[REDACTED]	[REDACTED]	[REDACTED]
[REDACTED]	[REDACTED]	[REDACTED]

Note: Only disease assessments collected in the CRF are included in the analysis.

* The new anti-cancer therapy information is only collected on the “Survival follow-up’ page but no date is collected. Consequently, it is assumed that the new therapy starts between the follow-up where the question “Did the patient start any new anti-cancer therapies?” is “Yes” and the previous follow-up. The subject will be censored at the last disease assessment prior or on this previous visit.

DOR will be summarized and listed by cohort and for CT and FDG-PET (=PET-CT) based responses separately. Duration of CR and duration of PR will be also reported separately.

DOR will be analyzed using Kaplan-Meier median, its 95% CI (and 25th and 75th percentile) and the estimates at 3, 6, 9, 12, etc months.

Theses analyses will be also repeated for the subgroups defined in Section 8.8.5 for the FAS.

